3.10 Statistical Considerations

3.10.1 General Statistical Considerations

All statistical analyses and data summaries are to be generated according to this SAP. Any deviations from this SAP will be documented in the Statistical Report and the CSR.

All statistical tests for the efficacy outcomes will be performed at one-sided 2.5% significance level, unless otherwise stated.

Summary statistics will be presented for the overall population as well as stratified by disease group and by site where appropriate.

3.10.2 Multiplicity

Along with the primary endpoint hypothesis (Sections 2.4.1 and 3.1) there are a total of 5 secondary endpoint hypothesis that will be tested. Alpha-inflation due to multiple

hypothesis testing is controlled by testing the secondary endpoints in a pre-specified hierarchy (Section 2.4.2) if and only if the primary endpoint hypothesis test meets statistical significance.

There are multiple interim looks proposed in the study design. Alpha-inflation here is controlled using the LDOF alpha-spending [2] function that determines how much of the total 2.5% alpha-level is to be spent at each interim look depending on the information fraction to be used at that particular interim. Thus at each interim analysis the alpha-level will be obtained using the LDOF spending function and this alpha-level will be used for the primary endpoint hypothesis testing as well the hierarchical testing of the secondary endpoints.

3.10.3 Missing Data

Missing data for the primary and secondary analysis can arise from different sources:

- 1. VFSS label: VFSS labels could be missing due to technical issues with the video and/or disagreement between the two independent central readers even after following procedures to resolve disgareements. Imputation of missing VFSS data for the primary and the secondary analysis will not be performed. The number of boluses with missing VFSS labels will be reported. Imputations considering "worst" and "best" case scenarios will be performed as supportive sensitivity analysis. For example, if the VFSS label is missing on one of the swallows then the worst case scenario will be to impute 1 (impaired) and the best will be to impute 0 (normal). In order to minimize missing VFSS labels, one extra swallow per consistency has been built into the protocol.
- 2. DSS Predicted Probability: The DSS outputs a predicted probability of impairment based on the input accelerometry signal. Due to technical reasons, the signal-t0noise-ratio (SNR) on these signals may be unusually high and in this case the DSS output may be missing. Again imputation of these missing values for the primary and secondary analysis will not be performed, rather the number of missing values will be reported. Sensitivity analysis using "worst" and "best" case scenarios will also be performed.

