3.7 Efficacy Analysis

Efficacy of the DDS screening device will be established if it's accuracy in terms of sensitivity and specificity with respect to VFSS to detect swallowing safety impairment are high, in particular, sensitivity has to be higher than 80% while the specificity has to be higher than 50%. The hypothesis test in equation (1) in Section 3.1 is to be tested for the primary endpoint hypothesis regarding the sensitivity and specificity using Thin-BA boluses as well as for secondary endpoints listed in Section 2.4.2. The secondary endpoint s will be tested in a hierarchical fashion if and only if the primary endpoint meets statistical significance. The hypothesis testing for primary and secondary endpoint will be carried out using the following test statistics

$$Z_{se} = \sqrt{N_d} \frac{\widehat{SE} - SE_0}{\sqrt{SE_0(1 - SE_0)}}; \text{ and}$$
$$Z_{sp} = \sqrt{N_h} \frac{\widehat{SP} - SP_0}{\sqrt{SP_0(1 - SP_0)}},$$

where N_d and N_h are the number of diseased and healthy subjects in the analysis dataset, $SE_0 = .8$ and $SP_0 = .5$. N_d and N_h will be determined solely based on the VFSS (gold-standard) results.

At each interim the above test statistics for sensitivity and specificity will be computed and the compared to the group-sequential boundary derived using the LDOF alpha-spending function separately for sensitivity and specificity. Thus the primary efficacy hypothesis will meet statistical significance if both Z_{se} and Z_{sp} cross their corresponding efficacy boundaries. If the primary endpoint sensitivity and specificity cross their corresponding boundaries then the secondary endpoints using the same test-statistics will be tested in the pre-specified hierarchy specified in Section 2.4.2. Note that group sequential boundaries are non-binding.

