3.9 Analysis Sets

3.9.1 Full Analysis Set (FAS)

The FAS is based on a modified-intent-to-treat ppulation which is defines as all subjects with a signed informed consent and at least one analyzable swallow with the Thin-BA boluses using the VFSS.

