3.12.5 Prevalence of Swallow Safety and Efficiency Impairments

Bolus level prevalence of Safety and Efficacy impairments will be summarized by swallow consistency and by swallow count. The number of missing VFSS label will also be summarized.

Subject level prevalence will also be reported similarly by swallow consistency and swallow count. Here, only the first impairment will be counted. Thus the prevalence at a particular swallow count is defined as the number of subjects showing their first impairment at that swallow count divided by the number of subjects at risk of impairment at that swallow. Cumulative prevalence will also be summarized.

Prevalence tables will also be reported stratified by primary diagnosis group and by site (in all 13 sites).

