0.35	0.85	0.65	0.74	0.625	0.258	525	1091	1300
0.45	0.85	0.65	0.65	0.741	0.406	525	1100	1300
0.55	0.85	0.65	0.57	0.829	0.538	525	1105	1300
0.65	0.85	0.65	0.48	0.881	0.614	525	1103	1300
0.35	0.92	0.55	0.56	0.705	0.342	525	1082	1300
0.45	0.92	0.55	0.62	0.647	0.275	525	1079	1300
0.55	0.92	0.55	0.64	0.580	0.192	525	1070	1300
0.65	0.92	0.55	0.63	0.481	0.098	876	1054	1300
0.35	0.92	0.58	0.41	0.969	0.828	525	1026	1300
0.45	0.92	0.58	0.46	0.941	0.803	250	1050	1300
0.55	0.92	0.58	0.50	0.908	0.734	525	1080	1300
0.65	0.92	0.58	0.54	0.836	0.580	525	1089	1300

Table 5-2: Simulation results under the Intersection Alternate Hypothesis for proposed group sequential design with thresholding at interim-1 and SSR at the last interim, for varying prevalence, sensitivity and specificity.

Prev.: Data generating prevalence

Se: Data generating Sensitivity

Sp: Data generating Specificity

Prop ChangeTH: Proportion of runs where threshold was changed at IA-1

Overall Power: Power to detect at least the primary hypothesis

Min.N, Avg.N, Max.N: All calculated over 10,000 $\,$

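### The SAP's worst and best cases for missing VFSS labels are prevalence extremes and do not bound sensitivity or specificity

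*SAP*

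**What the plan says.** SAP 3.10.3 does not impute missing VFSS labels in the primary or secondary analyses. It adds that worst and best "case scenarios will be performed as supportive sensitivity analysis". The rule is given as an example: "if the VFSS label is missing on one of the swallows then the worst case scenario will be to impute 1 (impaired"). A label of 0 is its best case. No other rule is given, and neither document ties the imputed label to the DDS result. Protocol 14.8.1 says only that there will be a sensitivity analysis.

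For missing DDS output, item 2 of the same section says "Sensitivity analysis using 'worst' and 'best' case scenarios will also be performed" and gives no direction.

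Three other places bear on this:

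- SAP 3.7 states that the numbers of diseased and healthy subjects "will be determined solely based on the VFSS (gold-standard) results".
- SAP 3.9.1 admits a subject to the full analysis set with "at least one analyzable swallow with the Thin-BA boluses using the VFSS". A subject with no MILD-Ba or MOD-Ba label can therefore be in the set.
- The rule that turns bolus labels into a subject's VFSS status is not stated for the endpoint. SAP 3.12.5 implies that any impaired bolus is enough: "Here, only the first impairment will be counted".

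**The concern.** Success requires sensitivity above 80% and specificity above 50% together. A worst case should push both down as far as the unknown labels allow. A label of 1 does not do that.

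Take a subject who is normal on every readable bolus and has one label missing. If the DDS was negative, imputing 1 turns a true negative into a false negative, which is unfavourable. If the DDS was positive, it turns a false positive into a true positive, which is favourable to both measures. A rule that ignores the DDS call mixes the two.

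The risk is in how the result will be read. A trial whose specificity is fragile to unreadable videos could report that it passed its worst case, when that scenario hardly tested specificity.

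**Working it through.** SAP 3.10.3 gives no figure to reproduce, so this is a reclassification of the two-by-two table.

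**Assumptions (the documents do not settle these).** A subject is impaired if any analysed bolus is impaired. Every subject has at least one label. The subject's DDS call does not change. Missingness is unrelated to DDS. Only VFSS-normal subjects can change status; let m of them have a residual missing label. Of these, m⁺ = m(1 − Sp) are DDS-positive and m⁻ = m·Sp are DDS-negative.

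**Formulas.**

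- All 0 (SAP best): Se = TP/n_d and Sp = TN/n_h, identical to no imputation.
- All 1 (SAP worst): Se = (TP + m⁺)/(n_d + m); Sp = (TN − m⁻)/(n_h − m) = Sp(n_h − m)/(n_h − m) = Sp, unchanged.
- Discordant with DDS: Se = TP/(n_d + m⁻); Sp = (TN − m⁻)/(n_h − m⁻).
- Concordant with DDS: Se = (TP + m⁺)/(n_d + m⁺); Sp = TN/(n_h − m⁺).
- Z statistics as in SAP 3.7, with null values 0.8 and 0.5.

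**Inputs.** N = 900 (SAP 3.2). Se 0.92, Sp 0.55 and prevalence 0.35 are one row of SAP Table 5-2. So n_d = 315, n_h = 585, TP = 289.8, TN = 321.75. The critical value is taken as 1.96. Without imputation, Z is 5.32 for sensitivity and 2.42 for specificity.

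**At m = 45** (m⁺ = 20.25, m⁻ = 24.75):

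- All 1: Se = 310.05/360 = 0.861, Z 2.91; Sp = 297/540 = 0.550, Z 2.32. Both pass.
- Discordant: Se = 289.8/339.75 = 0.853, Z 2.44; Sp = 297/560.25 = 0.530, Z 1.43. Specificity fails.
- Concordant: Se = 310.05/335.25 = 0.925; Sp = 321.75/564.75 = 0.570. The SAP's best case stays at 0.920 and 0.550.

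**Range over m** (estimate, Z in brackets):

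| m | All 1: Se | All 1: Sp | Discordant: Se | Discordant: Sp |
|---|---|---|---|---|
| 9 | 0.907 (4.81) | 0.550 (2.40) | 0.906 (4.73) | 0.546 (2.22) |
| 18 | 0.895 (4.32) | 0.550 (2.38) | 0.892 (4.14) | 0.542 (2.03) |
| 45 | 0.861 (2.91) | 0.550 (2.32) | 0.853 (2.44) | 0.530 (1.43) |
| 90 | 0.816 (0.78) | 0.550 (2.22) | 0.795 (−0.24) | 0.508 (0.39) |

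All-1 passes both measures while discordant labelling fails specificity for m from 22 to 64. At a critical value of 2.00 the range is 20 to 63. The O'Brien-Fleming-type final value is 1.98 to 2.00 for assumed looks at 0.22 and 0.60 to 0.70 of the information. At prevalence 0.45 and 1.96 the range is 12 to 89.

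**Is such an m plausible?** With the one spare THIN-Ba bolus, a subject falls short of four labels when at least 2 of 5 are missing. If losses are independent with rate q, the probability is 1 − (1 − q)⁵ − 5q(1 − q)⁴. At q = 5%, 8%, 10% and 14% this is 0.023, 0.054, 0.081 and 0.147, or 13, 32, 48 and 86 of 585 subjects. So m of 22 to 64 corresponds to losses of 6.6% to 11.8%. The protocol's figure is up to 14%, for safety or efficiency data.

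**Missingness related to DDS.** With 800 subjects, Se 0.86, Sp 0.60, prevalence 0.35 and m = 52, suppose 95% of the 52 are DDS-positive (49.4 positive, 2.6 negative). All-1 gives Se = (240.8 + 49.4)/332 = 0.874 and Sp = (312 − 2.6)/468 = 0.661. Both exceed the unimputed 0.860 and 0.600, so the SAP's worst case improves the result.

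**Subjects with no label at all.** Add 80 such subjects to the same 800, with DDS-positive rate 0.35 × 0.86 + 0.65 × 0.40 = 0.561. All-1 gives 0.794 and 0.600; all-0 gives 0.860 and 0.579. The best case then has lower specificity than the worst case.

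**The case against.** The strongest reply has four parts.

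**It is a supportive analysis, introduced as an example.** No test, boundary, stopping rule or sample-size re-estimation uses it. That is true and limits the weight of the point. But it is the only rule given and it says what the worst case will be, so it is what would be programmed.

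**The illustration is the least robust row for specificity.** Applying the same method at N = 900, prevalence 0.35 and 1.96 to other accuracy pairs, all-1 passes while discordant fails in these ranges:

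- Se 0.86, Sp 0.60 (the design assumption): m = 11 only
- Se 0.90, Sp 0.60: m = 36 to 41
- Se 0.92, Sp 0.58: m = 51 to 59
- Se 0.85, Sp 0.65: none

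In the first three, discordant labelling fails on sensitivity first. This stands. At this prevalence, misleading reassurance about specificity arises only when observed specificity is close to the 0.50 limit.

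**The SAP's rule sometimes raises the alarm anyway.** In the illustrated row, 14% independent loss gives m = 86, and all-1 then fails on sensitivity (0.819, Z 0.96). At 5% loss neither rule fails. Losses may also cluster within subjects: with an assumed within-subject correlation of 0.2, 10% loss gives m of about 74, where all-1 also fails. This also stands, so the damaging range is intermediate.

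**The fixed DDS call and the any-impaired rule are assumed.** If imputing a label brings that bolus's DDS output into the subject's call, the Z values shift and all-0 need not repeat the unimputed result. The figures depend on this. The underlying fault does not: a label imputed without reference to the DDS result does not bound accuracy.

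The spare bolus, third rater, consensus meeting and blinded monitoring of unreadable videos reduce m but do not change what the rule does.

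**Conclusion.** The concern holds. As written, SAP 3.10.3 labels prevalence extremes as worst and best cases for accuracy. Under the stated assumptions the best case adds nothing to the unimputed result. The worst case leaves expected specificity unchanged, and for sensitivity it is adverse but stops short of the true lower bound (by 0.8 points at m = 45).

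The conclusion changes for m from 22 to 64 when Se is 0.92, Sp 0.55 and prevalence 0.35. At the design assumption of 0.86 and 0.60 it hardly matters. The number of affected subjects, independence of losses, the any-impaired rule and the fixed DDS call are all assumptions, because the documents give no subject-level missingness.

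The undefined direction for missing DDS output and the unlabelled MILD-Ba and MOD-Ba subjects are lesser gaps; the conclusion does not rest on them. This should be corrected, but it does not touch the primary test, the boundaries or the sample-size re-estimation.

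**What to change.** Rewrite the paragraph in SAP 3.10.3 before unblinding, for all six endpoints:

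- **VFSS label missing.** Worst: the subject's status is set against the DDS call (impaired if DDS-negative, normal if DDS-positive), only where the observed labels leave it open. Best: set to agree with the DDS call.
- **DDS output missing.** Worst: opposite to VFSS. Best: equal to VFSS.
- **Subject-level rule.** State how bolus labels give the subject's VFSS status, and whether imputing a label changes which boluses feed the DDS call.
- **No label for a consistency.** State how these subjects are handled.
- Keep the all-1 and all-0 runs, renamed as high- and low-prevalence scenarios. Fully discordant labelling is an extreme, so a tipping-point analysis is a reasonable addition.

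The cost is one paragraph and minor programming. The reported worst-case figures will be less favourable. The primary analysis is unchanged.

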3.11 Interim Analysis Plans

The efficacy analysis steps at each of the interim looks are specified below. The steps are also summarized in Appendix 5.3

3.11.1 Interim Analysis - 1 (IA-1)

The main objective of IA-1 is to determine if the fixed threshold (fixed using phase-0 data) applied to the ROC curve obtained using IA-1 data is still optimal or whether a new threshold obtained from the IA-1 data should be used moving forward. In case the threshold is changed then the validation trial re-starts while excluding the IA-1 data for testing validation related hypotheses.

The Analysis plan for IA-1 are listed as follows:

- 1. Compute AUC for the ROC curve based on IA-1 data
- 2. If AUC < .75, consider futility analysis. Note that this futility rule is non-binding.
- 3. Otherwise, calculate sensitivity, specificity both with the fixed threshold from phase-0 data as well as the optimal threshold on the IA-1 ROC curve.
- 4. The benefit versus the cost of changing the threshold will be analyzed. This will be done by comparing the conditional power at IA-1 under the old threshold and a total sample size of N = 900 ($CP_{old,900}$) with the power of a restarted trial using the new threshold and sensitivity-specificity estimates obtained at IA-1 using this new threshold along with the prevalence estimate obtained at IA-1. If the power of the restarted trial with $N = 900 - N_1$ is greater than $CP_{old,900}$ then the benefit of changing the threshold is clear. Here N₁ is the number of subjects included in the IA-1 analysis. If this is not the case then the power of the restarted trial with N = 900 ($P_{new,900}$) will be compared to $CP_{old,900}$. Since conditional power and power will be calculated for testing both sensitivity and specificity for the primary endpoint the formal guideline (established using simulations) is defined in terms of the product of the two as follows:

If $P_{new,900-N_1,SE} \times P_{new,900-N_1,SP} > CP_{old,900,SE} \times CP_{old,900,SP}$ then change threshold; OR

If $P_{new,900,SE} \times P_{new,900,SP} > CP_{old,900,SE} \times CP_{old,900,SP} + 0.025$ then change threshold.

The above statistical logic offers a guideline for changing the threshold, however clinical justification may overrule the statistical guideline in this matter.

- 5. If the optimal threshold on the IA-1 ROC curve does not provide enough improvement in accuracies for the primary and secondary endpoints compared to the fixed thresholds then formal hypothesis test for the primary and secondary efficacy in the pre-specified order could be carried out at IA-1 and alpha is spent according to the LDOF spending function. If efficacy bounds are crossed for the primary and the first two secondary endpoints then the trial may be stopped early. In this case: stop enrollment and plan for the final analysis with the overruns.
- 6. If the hypothesis test results do not cross efficacy bounds then the trial continues as planned and moves to the next interim analysis.

As mentioned above, if the threshold is not updated using the IA-1 data then the trial continues to the second interim analysis (IA-2) or the first interim analysis for the newly started validation trial (IA-1ⁿ).

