3.1 Success Criteria and Hypothesis Testing

The success criteria for the DDS device validation trial is that the sensitivity is greater than 80% with a specificity greater than 50%. The sensitivity and the specificity will be estimated using an independent validation dataset. The following one-sided hypothesis testing will be carried out:

$$H_0 : H_0^{se} \cup H_0^{sp} \text{ vs.}$$

$$H_A : H_A^{se} \cap H_A^{sp},$$
(1)

where,

 $\begin{array}{lll} H_0^{se} & : & \mathrm{Sensitivity} \leq .8, \\ H_A^{se} & : & \mathrm{Sensitivity} > .8, \\ H_0^{sp} & : & \mathrm{Specificity} \leq .5, \text{ and} \\ H_A^{sp} & : & \mathrm{Specificity} > .5. \end{array}$

Each of H_0^{se} vs. H_A^{se} and H_0^{sp} vs. H_A^{sp} will be tested at one-sided 2.5% level of significance which will (conservatively) preserve the over-all type-I error for testing H_0 vs. H_A .

The same hypothesis test as in (1) will be applied to the secondary endpoints. Hypothesis will be carried out in a hierarchical fashion to ensure that the type-I error is controlled at the one-sided 2.5% level.

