3.5 Group Sequential Design and Sample Size Re-estimation Details

Due to uncertainties about the population parameters and their influence on the power, an adaptive sample size re-estimation (SSR) is proposed. This is after the first interim the trial continues as a 3-look GSD with out changing the threshold then a SSR would be done at the second interim analysis while if the threshold is changed at the first interim then the SSR will be carried out at the only interim analysis time for the freshly started validation trial post threshold re-calibration. The following adaptation rules will be applied:

- 1. If the threshold is changed based on the first interim look, then a new appropriately powered (80%-90%) 2-look group sequential design trial will be started. The powering will be based on the sensitivity and specificity estimates obtained at the first interim. The interim and the final analysis for this new trial would not include the data from subjects included in the first interim analysis.
- 2. At the interim of the new validation trial, unless the interim Z statistic crossed the efficacy boundary, a sample size re-estimation based on conditional power being in the promising zone [1] will be carried out. Conditional power (CP) will be calculated both for sensitivity as well as specificity. Promising zone is defined as both the CPs are between 50% and 90%. Futility may also be decided in case of low conditional power for either sensitivity or specificity.
- 3. The increase will be determined equating CP to the desired power of 90%. This will be bracketed by a minimum increase of 50 subjects and max increase defined by the maximum sample size of 1300.
- 4. In case the threshold is not changed at the first interim, the trial continues as a 3-look GSD and the SSR adaptation rules in 2-3 above will apply at the second interim look.

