3.11.2 IA-2 (or IA- 1^n)

- 1. Test primary and secondary efficacy hypotheses in the pre-specified hierarchy. If efficacy boundaries for the primary and the first two secondary endpoints are crossed then the trial may be stopped early and the final analysis is planned with the overruns
- 2. If the efficacy boundaries for the primary endpoint and the first two secondary endpoints (i.e. for sensitivities and specificities for detecting impaired safety with Thin-BA, Mild-BA and Moderate-BA) are not crossed then consider sample size re-estimation (SSR) using the promising zone approach (Mehta and Pocock, 2011, Statistics in Medicine).
 - Calculate conditional power (CP) for sensitivities and specificities for the primary efficacy (Thin-safety). If $0.5 \leq CP \leq 0.9$ then increase sample size to meet CP = 0.9 up to a maximum of 1300 subjects overall (including the IA-1 subjects)
 - If CP < 0.5 or CP > 0.9 then the trial continues as planned.
 - If CP < 0.2 then consider futility

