5.1 Simulations with Sample Size Re-estimation

Simulations for the proposed GSD with SSR in Section 5 were carried out under the null hypothesis (sensitivity $\leq .8$ and/or specificity $\leq .5$) while varying the prevalence from 35% to 65%. Power from 10,000 monte-carlo runs for different combinations of sensitivity and specificity in Table 8-1 show that the type-I error is preserved at the 2.5%.

Simulations under the alternative (sensitivity > .8 and specificity > .5 for the primary and the first two secondary endpoints) show that for prevalence varying between 35% and 65%, sensitivity around 90% and specificity greater than 60% the power achieved is greater than 90% for a expected sample size between 950 and 1050 subjects under the adaptive group sequential design.

Prev.	Se	Sp	Prop. ChangeTH	Prop. Futility stop at IA1	Overall Power	Min.N	Avg.N	Max.N
0.35	0.80	0.50	0.05	0.93	0.0004	876	882	1300
0.50	0.80	0.50	0.05	0.94	0.0001	876	882	1300
0.65	0.80	0.50	0.07	0.92	0.0000	876	884	1300
0.35	0.85	0.50	0.19	0.77	0.0094	876	904	1300
0.50	0.85	0.50	0.18	0.78	0.0106	876	904	1300
0.65	0.85	0.50	0.21	0.75	0.0137	876	909	1300
0.35	0.90	0.49	0.40	0.57	0.0150	876	930	1300
0.50	0.90	0.49	0.39	0.58	0.0160	876	929	1300
0.65	0.90	0.49	0.40	0.57	0.0144	876	931	1300
0.35	0.80	0.55	0.16	0.78	0.0088	876	900	1300
0.50	0.80	0.55	0.16	0.80	0.0067	876	899	1300
0.65	0.80	0.55	0.19	0.77	0.0046	876	902	1300
0.35	0.79	0.60	0.33	0.63	0.0062	876	916	1300
0.50	0.79	0.60	0.35	0.61	0.0052	876	919	1300
0.65	0.79	0.60	0.35	0.62	0.0037	876	918	1300

Table 5-1: Simulation results under the Union Null Hypothesis for proposed group sequential design with thresholding at interim-1 and SSR at the last interim, for varying prevalence, sensitivity and specificity.

Prev.: Data generating prevalence

Se: Data generating Sensitivity

Sp: Data generating Specificity

Prop ChangeTH: Proportion of runs where threshold was changed at IA-1

Prop. Futility Stop at IA-1: Futility Futility stopping triggered at IA-1, however simulations carried out under non-binding futility

Overall Power: Power to detect at least the primary hypothesis

Min.N, Avg.N, Max.N: All calculated over 10,000 runs with non-binding futility

Prev.	Se	Sp	Prop. ChangeTH	Overall Power	Power to Reject All 3 endpoints	Min.N	Avg.N	Max.N
0.35	0.90	0.60	0.34	0.995	0.894	250	969	1300
0.45	0.90	0.60	0.33	0.993	0.903	250	946	1300
0.55	0.90	0.60	0.33	0.979	0.901	250	989	1300
0.65	0.90	0.60	0.36	0.947	0.829	250	1044	1300

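### The restart after IA-1 is judged and sized on uncorrected accuracy from the same subjects who chose the threshold; an optimism correction is a cheap, modest gain

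*SAP*

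**What the plan says.** SAP 3.11.1 step 3 calculates sensitivity and specificity at the phase-0 threshold "as well as the optimal threshold on the IA-1 ROC curve". Step 4 sets conditional power under the old threshold at 900 subjects against the restart, that is, "with the power of a restarted trial using the new threshold and sensitivity-specificity estimates obtained at IA-1 using this new threshold", together with the IA-1 prevalence. The threshold changes in either of two cases:

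- the product of the two restart powers at 900 - N1 exceeds the product of the two conditional powers;
- the restart product at 900 exceeds it by more than 0.025.

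SAP 3.5 item 1 adds that after a change "then a new appropriately powered (80%-90%) 2-look group sequential design trial will be started", and "The powering will be based on the sensitivity and specificity estimates obtained at the first interim". IA-1 subjects are then excluded from the validation. SAP 3.4 puts IA-1 at about 200 subjects. SAP 3.11.2 allows a later sample size re-estimation (SSR) "up to a maximum of 1300 subjects overall (including the IA-1 subjects").

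Neither document defines the criterion for the optimal threshold or names a bootstrap, cross-validation or shrinkage step for the IA-1 estimates.

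**The concern.** The same roughly 200 subjects, about 70 of them impaired at 35% prevalence, choose the threshold, supply its accuracy and size the next trial. Such resubstitution estimates are too high on average, because the selected cut-point partly follows chance in the sample. Conditional power under the old threshold uses a cut-point fixed beforehand and is free of this. The two sides of the inequality are therefore not on the same footing, and the first inequality carries no margin.

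Two things are at stake. Some threshold changes, each of which discards the IA-1 data, would be made that corrected figures do not support. The iDMC would also see a restart power that is too high on average. This concerns efficiency only.

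**Working it through.** **Inputs.** Each hypothesis "will be tested at one-sided 2.5% level of significance" (SAP 3.1). The nulls are 0.80 and 0.50 (3.1), prevalence is 0.35 (3.2), and N1 is about 200 (3.4), with 250 also run. The starting size is 900 and the cap 1300 (3.2, 3.5).

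**Power formula, from the Z statistics in SAP 3.7.** Power = Φ{[(p1 - p0)√n - 1.96√(p0(1 - p0))] / √(p1(1 - p1))}, with n = 0.35N for sensitivity and 0.65N for specificity. Joint power is the product.

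**Reproducing the plan's figures.**
- At N = 900 the formula tracks Table 5-2 (prevalence, Se/Sp: formula against table): 0.35, 0.90/0.60: 0.998 against 0.995; 0.35, 0.85/0.65: 0.614 against 0.625; 0.65, 0.85/0.65: 0.883 against 0.881; 0.35, 0.92/0.58: 0.973 against 0.969; 0.35, 0.92/0.55: 0.678 against 0.705.
- The 90% at 700 to 800 subjects in SAP 3.2 is not reproduced. At 0.86/0.60 the formula gives 0.666 at 700 and 0.734 at 800. That is a separate matter.

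**Why small optimism matters.** Take N = 700, so 245 impaired and 455 healthy.
- At 0.86: (0.06 × 15.652 - 0.784)/0.347 = 0.447, power 0.673. At 0.60: (0.10 × 21.331 - 0.98)/0.490 = 2.354, power 0.991. Product 0.666.
- Add 1.5 and 0.7 points. At 0.875: (0.075 × 15.652 - 0.784)/0.331 = 1.179, power 0.881. At 0.607: power 0.996. Product 0.877.

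**Simulation.** 4,000 trials per cell, equal-variance binormal scores, threshold maximising the power product, and the phase-0 threshold set to the stated Se/Sp. The AUC gate of 0.75 and both SAP inequalities are applied. Old-threshold conditional power follows the observed trend. The correction is 50 bootstrap resamples stratified by VFSS status, reselecting the threshold each time. SSR is included and early stopping is not.

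Optimism in sensitivity/specificity is 1.3-1.5 / 0.6-0.7 points at N1 = 200 and 1.0-1.1 / 0.4-0.6 at N1 = 250. With Youden's index as the criterion it was 3.7 / 1.9 points at 0.86/0.60, N1 = 200.

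Mean power of a 700-subject restart, N1 = 200:

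| Se/Sp | Calculated | Corrected | True | Gap (points) | Share removed |
|---|---|---|---|---|---|
| 0.90/0.60 | 0.915 | 0.866 | 0.826 | 8.9 | 55% |
| 0.86/0.60 | 0.716 | 0.627 | 0.507 | 20.9 | 43% |
| 0.85/0.65 | 0.828 | 0.757 | 0.678 | 15.0 | 47% |
| 0.92/0.58 | 0.947 | 0.909 | 0.892 | 5.5 | 69% |
| 0.92/0.55 | 0.908 | 0.855 | 0.826 | 8.2 | 65% |

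Gap is calculated minus true; share removed is (calculated - corrected)/gap.

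Threshold changes, as written → corrected (N1 = 200; N1 = 250): 0.90/0.60: 60→45%; 50→38%. 0.86/0.60: 71→54%; 68→52%. 0.92/0.55: 87→78%; 85→79%.

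Overall success with SSR, restarts sized for 90% joint power but not below 876 in total. The floor is the Min.N of Table 5-1, whose footnote reads "Min.N, Avg.N, Max.N: All calculated over 10,000 runs with non-binding futility".

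| Se/Sp | N1 = 200 | N1 = 250 |
|---|---|---|
| 0.90/0.60 | 0.882→0.904 | 0.900→0.916 |
| 0.86/0.60 | 0.680→0.711 | 0.718→0.738 |
| 0.85/0.65 | 0.796→0.801 | 0.800→0.816 |
| 0.92/0.58 | 0.922→0.932 | 0.930→0.937 |
| 0.92/0.55 | 0.863→0.866 | 0.873→0.879 |
| 0.82/0.70 | 0.744→0.750 | 0.773→0.778 |

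Gains are 0.3 to 3.1 points (SE of the paired gain 0.1 to 0.5). With restarts fixed at 900 - N1 or 900 they are -1.0 to +4.1. A repeat of 4,000 trials per cell gave +0.2 to +3.7 (sized) and -0.9 to +3.7 (fixed), with mean total N changing by -11 to +39.

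**What the correction does not remove.** True power before SSR of restarts sized for 90% barely moves: 0.778→0.788 at 0.90/0.60, N1 = 200. In a run at 0.86/0.60 without SSR and with restarts at the rule sizes, never changing gave success of about 0.79, the rule 0.60 and the corrected rule 0.64. Most of the loss is noise in a threshold chosen on about 70 impaired subjects.

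**Does Table 5-2 already cover this?** Its footnote defines only "Se: Data generating Sensitivity" and the matching specificity. With N1 = 250 and an impaired-group SD of 1/1.5, modelled power over the 16 rows differs from the table by 3.9 points on average (maximum 8.1) if a restart keeps the row's Se/Sp. It differs by 11.0 (maximum 31.6) if the restart takes the chosen threshold's true accuracy. At prevalence 0.35, 0.90/0.60, the table gives 0.995 and the model 0.992 or 0.879. So the table may leave out the effect of choosing the threshold on IA-1 data. This is an inference; the SAP does not say.

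**The case against.** **The SAP does not name the estimator.** A cross-validated IA-1 estimate would fit its wording, and the protocol synopsis describes 10,000 random 80:20 splits for the phase-0 threshold. But those splits concern phase 0 only, and nothing requires held-out estimation at IA-1.

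**Safeguards exist.** The guideline is said to rest on simulations, one inequality has a 0.025 margin, clinical judgement may overrule it, IA-1 data are dropped after a change, and SSR follows on fresh data. All true, and they keep this a minor point. However, the margin covers only one inequality, any override would weigh an inflated restart power, and the success gains above already include SSR.

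**The gain is concentrated where the phase-0 threshold was adequate.** This stands in large part. At 0.82/0.70 the gain is 0.5 to 0.6 points sized, with a loss of 1.0 when restarts are fixed at 900. A smaller run (1,500 trials) gave -2.5 points there (SE 1.3); the 4,000-trial repeat gave +0.7 sized and -0.9 fixed. With phase-0 thresholds at 0.80/0.69 or 0.84/0.71, restarts sized to 90% and no 876 floor, corrected sizing gained 4 to 7 points for about 65 to 80 more subjects on average. At the rule sizes the gain was about zero.

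**A larger margin would also reduce changes.** Adding 0.10 to both inequalities gained 5.9 points at 0.90/0.60 and 7.6 at 0.86/0.60, but lost 6.4 at 0.82/0.70. That sets a preference about how readily to change. The correction removes a bias in a planning figure, and its downside is much smaller.

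**The size is model-dependent.** This stands. At N1 = 250 and prevalence 0.35, modelled change rates are 50% against a listed 34% at 0.90/0.60, and 85% against 56% at 0.92/0.55. A null-variance form of the old-threshold conditional power moves the success gains to between -0.7 and +6.5 points.

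**Conclusion.** The concern holds as an optional improvement, with medium confidence. Restart power is overstated by about 6 to 21 points on average at 700 subjects, and correction removes roughly half. Overall success gains 0.3 to 3.1 points when restarts are sized for 90%, and changes by -1.0 to +4.1 at the fixed rule sizes. Other choices leave the direction the same: maximising the smaller margin instead of the power product gave +1.1 to +3.0 at 0.90/0.60 and 0.86/0.60, and an impaired-group SD of 1/1.5 gave +0.6 to +2.6 at N1 = 250.

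The figures assume binormal scores, a stated threshold criterion, trend-based conditional power, sizing to a product of 0.90 and no early stopping. The direction is firmer than the size. Type I error and the final estimates are not in question.

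**What to change.** In SAP 3.11.1 step 3, state the criterion that makes a threshold optimal. In 3.11.1 step 4 and 3.5 item 1, compute restart power and restart size from optimism-corrected IA-1 sensitivity and specificity. The corrected value is the apparent value minus the mean optimism over bootstrap resamples stratified by VFSS status, with the threshold reselected in each resample. Optimism in a resample is the accuracy of its chosen threshold in that resample minus the accuracy of the same threshold in the IA-1 data. Cross-validation that repeats the selection would also serve.

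The cost is two SAP sentences and a few lines of code at the independent statistical center, with no new data and no change to the tests. Expect fewer threshold changes, and a calculated restart about 40 to 50 subjects larger within the 1300 cap (759→800 at 0.90/0.60 and 903→954 at 0.86/0.60, N1 = 200). Where the phase-0 threshold is misplaced, a small loss is possible, at most 1.0 point in the main simulation.
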